11.4 Vital signs, physical findings, and other observations related to safety

11.4.1 Vital signs

The following vital signs measurements will be obtained:

- Systolic and diastolic blood pressure
- Pulse rate
- Temperature (oral, axillary, or otic)

A by-subject listing of all vital sign measurements and changes from Baseline will be presented by treatment group and visit. The listing will include a flag for measurements identified as TEMA/potentially clinically significant (PCS) as calculated by the criteria outlined in [Table 14–10](#). Body weight will also be included in the listing.

Descriptive statistics will be reported for all vital sign measurements (with the exception of body weight). Observed values and changes from Baseline will be summarized by treatment group for each vital signs variable and visit.

Figures of mean change from Baseline over time will be presented for each variable by treatment group.

The number and percentage of subjects with TEMA/PCS vital sign values will be summarized by treatment group at each visit. The denominator for the percentage calculations will be the number of subjects with a non-missing measurement for the variable at the specific visit.

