4.3 Safety variables

4.3.1 Secondary safety variables

Safety variables to be assessed are:

- Frequency and severity of AEs and SAEs
- Withdrawal due to AEs
- Change from Baseline in vital signs (blood pressure [BP] and pulse rate) and body weight
- Changes from Baseline in ECG parameters
- Change from Baseline in clinical laboratory parameters (hematology, biochemistry, and urinalysis)
- Change from Baseline in physical examination

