11.3.6 Body weight

Body weight, including height and BMI, will be collected at the visits specified in [Table 5-1](#). The same scale for measuring body weight should be utilized throughout the study where possible.

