2.2.3 Safety variables

As part of the secondary objective, the following secondary safety variables will be assessed:

- Frequency and severity of adverse events (AEs) and serious adverse events (SAEs)
- Withdrawal due to AEs
- Change from Baseline in vital signs (blood pressure, pulse rate and body temperature) and body weight
- Change from Baseline in electrocardiogram (ECG) parameters
- Change from Baseline in clinical laboratory parameters (hematology, biochemistry, and urinalysis)
- Change from Baseline in physical examination

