14.8 Treatment-emergent markedly abnormal vital signs values

The criteria for identifying TEMA/PCS vital signs values are provided in [Table 14–10](#).

Table 14–10: TEMA/PCS criteria for vital signs

Variable	Unit	Low ^a	High ^a
Systolic blood pressure	mmHg	Value ≤90 and ≥30 decrease from Baseline	Value ≥180 and ≥40 increase from Baseline
Diastolic blood pressure	mmHg	Value ≤50 and ≥20 decrease from Baseline	Value ≥105 and ≥30 increase from Baseline
Pulse rate	bpm	Value ≤50 and ≥30 decrease from Baseline	Value ≥120 and ≥30 increase from Baseline

bpm=beats per minute.

Note: the change in measurement (increase or decrease) will be calculated relative to the value obtained at Baseline.

^a Both conditions must be satisfied for a measurement to be considered PCS.

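### Change in body weight is a named secondary safety variable, but the SAP excludes weight from summary statistics, so no by-arm summary of it is planned

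*SAP*

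**What the plan says.** Protocol 4.3.1, the list of secondary safety variables, includes "Change from Baseline in vital signs (blood pressure [BP] and pulse rate) and body weight". SAP 2.2.3 keeps the item and adds temperature: "Change from Baseline in vital signs (blood pressure, pulse rate and body temperature) and body weight".

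On collection, Protocol 11.3.6 says "Body weight, including height and BMI, will be collected at the visits specified in" Table 5-1. That table marks body weight at Screening, Baseline, Week 12 and the SFU/Early Withdrawal visit.

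On output, SAP 11.4.1 says three things that matter here:

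- For the listing: "Body weight will also be included in the listing".
- For summary statistics: "Descriptive statistics will be reported for all vital sign measurements (with the exception of body weight").
- For change from Baseline: "Observed values and changes from Baseline will be summarized by treatment group for each vital signs variable and visit". The measurements listed at the top of that section are systolic and diastolic blood pressure, pulse rate and temperature. Weight is not among them.

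**The concern.** The SAP commits in one section to assessing change in body weight, and in another rules out the statistics that would report it. A by-subject listing prints individual values. It gives no mean, spread or median by arm, so it does not show whether weight moved differently under bimekizumab, adalimumab or placebo.

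At stake is the completeness of the secondary safety reporting. If the SAP is followed, the clinical study report has no planned arm-level figure for a variable named in advance. Any summary produced later would be an unplanned addition.

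**Working it through.** No arithmetic applies, and the documents give no figure to reproduce. The check is to follow body weight through both documents and see whether any section supplies a by-arm summary of its change.

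| Place | What it provides for body weight |
|---|---|
| Protocol 4.3.1 | Change from Baseline is a secondary safety variable |
| Protocol Table 5-1 and 11.3.6 | Measured at Screening, Baseline, Week 12 and SFU/Early Withdrawal; same scale to be used where possible |
| Protocol 15.8 | All safety variables to be analysed on the Safety Set; weight is not named among the items presented descriptively; only C-SSRS is marked as listed only |
| SAP 2.2.3 | Change from Baseline is again a secondary safety variable |
| SAP 3.1 | General rule: continuous variables are summarised by treatment and, where applicable, visit |
| SAP 3.9 | No entry about body weight |
| SAP 6.2 | Screening weight summarised by arm as a demographic characteristic |
| SAP 11.4.1 | Listing included; descriptive statistics expressly excluded |
| SAP 14.8, Table 14-10 | Criteria for systolic pressure, diastolic pressure and pulse rate only |

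The reasoning runs in four steps.

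1. **The variable can be derived.** Weight is scheduled before dosing and at two later points. SAP 3.3 defines Baseline generally as the last value before the first dose. Change to Week 12 and to SFU therefore needs no further data.
2. **The general rule would have covered it.** Weight is continuous, so SAP 3.1 on its own would lead to a summary by treatment and visit. The exception in SAP 11.4.1 is what removes it.
3. **Nothing else fills the gap.** The by-arm summaries and figures of change in SAP 11.4.1 follow its list of vital signs, which omits weight. Table 14-10 has no weight criterion, so there is no count of marked abnormalities either. The one arm-level weight summary, in SAP 6.2, is of Screening weight and says nothing about change.
4. **The exclusion is not declared.** SAP 3.9 records departures as small as revised terminology in the HiSCR definition, but not this one. The list of SAP amendments in section 15 does not mention it.

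Planned by-arm summaries of change in body weight: none.

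**The case against.** The strongest reply is that no protocol-specified table has been removed. Protocol 15.8 names the data to be presented descriptively by treatment group, and weight is not among them. Protocol 11.3.3 defines vital signs as blood pressure, pulse rate and temperature, with weight treated separately in 11.3.6. The sentence about analysing all safety variables can be read as fixing the population rather than the type of output. The safety variables in the protocol's Summary (section 1) also omit weight. On this reading, the missing SAP 3.9 entry is only a documentation point.

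This partly stands. The conflict rests mainly on the two secondary-variable lists, not on the descriptive-presentation sentence in 15.8. But 15.8 does say all safety variables will be analysed, and it marks C-SSRS alone as listed only. The disagreement between SAP 2.2.3 and SAP 11.4.1 lies within one document and does not depend on how 15.8 is read.

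Three further points can be made:

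- **The data are still reported.** True: values appear in a listing ordered by treatment group. A listing is still not an arm-level summary.
- **Other items are treated the same way.** Change in physical examination is in the same secondary list, and SAP 11.4.3.1 only lists abnormalities. That is a parallel gap and does not close this one.
- **The consequence is low.** True: weight is not an adverse event for special monitoring, and a weight change reported as a treatment-emergent adverse event would enter the by-arm adverse event tables.

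**Conclusion.** The concern holds. The current SAP text gives a named secondary safety variable no planned by-arm summary, although the measurements are scheduled and the SAP's own general rule would have produced one. It affects one component of one item in the safety list, for a planned 80 subjects. The primary efficacy analysis, the success criterion and the other vital-sign summaries are untouched.

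This is a minor point, worth correcting because the correction is almost free. The conclusion assumes that the SAP is followed as written and that no output document outside the protocol and SAP adds the summary.

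**What to change.** In SAP 11.4.1, delete the exception for body weight and add a sentence providing for descriptive statistics of observed weight and change from Baseline, by treatment group, at Week 12 and SFU, on the Safety Set. Deleting the parenthesis alone may not be enough, because the list of measurements at the top of the section omits weight. A separate sentence is cleaner than extending that list, which would also bring weight into the figures of mean change. The Baseline definition in SAP 3.3 and the early-withdrawal visit mapping in SAP 4.4 can be used unchanged.

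The cost is about one extra row in an existing table, with no new data or visits.

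If the sponsor prefers to keep weight as a listing only, the minimum is to record that choice and its reason in SAP 3.9 and to align SAP 2.2.3 with it. That resolves the inconsistency but still leaves the variable without a by-arm result.

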11.4.2 Electrocardiograms

Standard 12-lead ECG recordings will be obtained after 10 minutes of rest in the supine position. The following ECG variables will be reported together with the Investigator's interpretation of the ECG profile:

- PR interval
- QRS interval
- QT interval
- Heart rate
- QT corrected for heart rate using Fridericia's formula (QTcF)

The results of all ECG variables will be reported in the by-subject listings. The listing will also include the changes from Baseline and percentage changes from Baseline and will be presented by treatment group and visit.

Observed values, changes and percentage changes from Baseline will be summarized for each variable by treatment group and visit.

The following cut points in QTcF (raw data and change from Baseline) will be summarized categorically by treatment group (number and percentage of subjects) and visit. The denominator

for the percentage calculations will be the number of subjects with a non-missing measurement for the variable at the specific visit.

Observed QTcF data:

- <450msec
- ≥450msec to <480msec
- ≥480msec to <500msec
- ≥500msec

Change from Baseline QTcF:

- <30msec
- ≥30ms to <60msec
- ≥60msec

Electrocardiogram findings including the Investigator's interpretation of the ECG profile will be listed separately.

11.4.3 Other safety variables

11.4.3.1 Physical examination

Subjects with abnormalities in the physical examination will be listed including details of the abnormality.

11.4.3.2 Columbia-Suicide Severity Rating Scale

The C-SSRS is divided into 2 time intervals and further sub-divided as shown:

- *C-SSRS at Baseline* – assessed at the Screening visit
 - Suicidal Ideation – over Lifetime and over Past 6 Months
 - Intensity of Ideation – over Lifetime and over Past 6 Months
 - Suicidal Behavior – over Lifetime and over Past 2 Years
- *C-SSRS Since Last Visit* – assessed at all visits after Screening
 - Suicidal Ideation – Since Last Visit
 - Intensity of Ideation – Since Last Visit
 - Suicidal Behavior – Since Last Visit

For Suicidal Ideation questions, only those questions where “Yes” has been answered will be listed. For Intensity of Ideation questions and Suicidal Behavior questions, any question for which an answer has been recorded will be listed.

Results, as specified above, will be listed for each subject and visit.

11.4.3.3 Chest X-ray and tuberculosis questionnaire

The results of the chest X-ray (or computed axial tomography scan if applicable), TB questionnaire and TB test will be listed for each subject.

12 OTHER ANALYSES

A listing of comments will be provided, if applicable. This will be based on the RS.

This document cannot be used to support any marketing authorization application and any extensions or variations thereof.

PUBLIC COPY

14 APPENDICES

14.1 HS-Physician's Global Assessment 6-point scale

The HS-Physician's Global Assessment 6-point scale is scored according to the specifics in [Table 14-1](#).

Table 14-1: HS-Physician's Global Assessment 6-point scale

Score	Rating	Description
0	Clear	No abscesses, no draining tunnels (fistulas/sinus tracts), no nodules
1	Minimal	No abscesses, no draining tunnels (fistulas/sinus tracts), no inflammatory nodules, presence of non-inflammatory nodules
2	Mild	No abscesses or draining tunnels (fistulas/sinus tracts), and less than 5 inflammatory nodules, or Single abscess or draining tunnel (fistula/sinus tract), and no inflammatory nodules
3	Moderate	No abscesses or draining tunnels (fistulas/sinus tracts), and at least 5 inflammatory nodules, or Single abscess or draining tunnel (fistula/sinus tract) in the presence of inflammatory nodules, or Between 2 and 5 abscesses or draining tunnels (fistulas/sinus tracts) with or without inflammatory nodules, up to 10
4	Severe	Between 2 and 5 abscesses and draining tunnels (fistulas/sinus tracts), with inflammatory nodules that are greater than 10
5	Very severe	More than 5 abscesses or draining tunnels (fistulas/sinus tracts)

14.2 Modified Sartorius Score

The scoring system for the presence, counts and measurements of relevant lesions by type are given in [Table 14-2](#).

Table 14-2: Modified Sartorius Score

Characteristics of HS lesions	Points
Anatomical region	
Any	3
None	0
Types of lesions	
Fistula ^a	4
Nodule ^b	2
Abscess	1
Scar ^c	1

Table 14–2: Modified Sartorius Score

Characteristics of HS lesions	Points
Other ^d	1
Total area involved^e	
< 5 cm	2
5 to 10 cm	4
> 10 cm	8
Are all lesions clearly separated by normal skin?^f	
Yes	0
No	6

HS=hidradenitis suppurativa

Taken from <http://cursoenarm.net/UPTODATE/contents/mobipreview.htm?36/33/37400> and adapted from:

^a Fistula includes draining tunnels (fistulas/sinus tracts)

^b Nodule refers to inflammatory nodules

^c Scar refers to hypertrophic scars

^d Other includes non-inflammatory nodules and non-draining tunnels (fistulas/sinus tracts).

^e Area is defined as the longest distance between 2 relevant lesions (ie, abscess, draining tunnel (fistula/sinus tract) or inflammatory nodule). If there is only 1 lesion it is the measurement of the single lesion diameter.

^f This refers to all relevant lesions.

14.3 Dermatology Life Quality Index

The 10 questions and scoring of the DLQI are presented in [Table 14–3](#).

Table 14–3: Dermatology Life Quality Index

Item Nr.	Question	Answers
1	Over the last week, how itchy, sore painful or stinging has your skin been?	Very much
		A lot
		A little
		Not at all
2	Over the last week, how embarrassed or self-conscious have you been because of your skin?	Very much
		A lot
		A little
		Not at all

Table 14–3: Dermatology Life Quality Index

Item Nr.	Question	Answers
3	Over the last week, how much has your skin interfered with you going shopping or looking after your home or garden?	Very much
		A lot
		A little
		Not at all
		Not relevant
4	Over the last week, how much has your skin influenced the clothes you wear?	Very much
		A lot
		A little
		Not at all
		Not relevant
5	Over the last week, how much has your skin affected any social or leisure activities?	Very much
		A lot
		A little
		Not at all
		Not relevant
6	Over the last week, how much has your skin made it difficult for you to do any sport?	Very much
		A lot
		A little
		Not at all
		Not relevant
7	Over the last week, has your skin prevented you from working or studying? If "No", over the last week how much has your skin been a problem at work or studying?	Yes
		No
		Not relevant
		A lot
		A little
		Not at all
8	Over the last week, how much has your skin created problems with your partner or any of your close friends or relatives?	Very much
		A lot
		A little
		Not at all

Table 14–3: Dermatology Life Quality Index

Item Nr.	Question	Answers
		Not relevant
9	Over the last week, how much has your skin caused any sexual difficulties?	Very much
		A lot
		A little
		Not at all
		Not relevant
10	Over the last week, how much of a problem has the treatment for your skin been, for example by making your home messy, or by taking up time?	Very much
		A lot
		A little
		Not at all
		Not relevant

The following rules apply to the scores for the individual questions and the calculation of the total DLQI score:

[figure not shown]
- Individual responses will be scored as follows, with separate rules for Question 7 below:
 - Very much = 3
 - A lot = 2
 - A little = 1
 - Not at all = 0
- If 1 question is left unanswered this question will be scored as 3 and the scores for each question will be summed to give the total DLQI score.
- If two or more questions are left unanswered a total DLQI will not be calculated.
- If Question 7 is answered “Yes” this will be scored as 3. If question 7 is answered “No” the scoring will be as follows:
 - If “A lot”, “A little” or “Not at all” is ticked this will be scored as 2, 1 or 0 respectively.
 - If the second half of the questions is left incomplete, the score will be set to 3.
- If a question is answered as “Not relevant” then this will be scored as 0.
- If two or more response options are ticked, the response option with the highest score will be recorded.
- If there is a response between two tick boxes, the lower of the two score options will be recorded.

- The total DLQI score will be calculated by summing the scores over all the questions.

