8.3.6 Dermatology Life Quality Index

The DLQI is a questionnaire designed for use in adult subjects with inflammatory skin diseases and has been used in patients with HS (Finlay, 1998; Esmann et al, 2010; Basra et al, 2012). The DLQI is a skin disease specific questionnaire aimed at the evaluation of how symptoms and treatment affect subjects' health related quality of life (QoL).

This instrument asks subjects about symptoms and feelings, daily activities, leisure, work and school, personal relationships and treatment. The total DLQI score ranges from 0 to 30 with higher scores indicating lower health related QoL. The complete questionnaire is shown in [Section 14.3](#) together with the scoring and derivation of the total DLQI.

Each question on the DLQI will be listed by treatment group and subject for each visit. The listing will also include the total DLQI score at each visit together with the changes from Baseline in the total DLQI score. Summary statistics will be presented for the observed total DLQI score at each visit together with the changes from Baseline in the total DLQI score by treatment group, overall and by Baseline Hurley Stage.

The number and percentage of subjects with a total DLQI score in each of the following categories will be summarized at each visit, by treatment group, overall and by Baseline Hurley Stage:

- Total DLQI score of 0 or 1

- Change from Baseline in the total DLQI score of -4 or below

For the summary of the change from Baseline in the total DLQI score of -4 or below, the denominator for the percentages will be the number of subjects with non-missing data and who had a total DLQI score of 4 or higher at Baseline.

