14.5 Hospital Anxiety and Depression Scale

The individual items on the HADS-A and HADS-D scales are listed in [Table 14–6](#).

Table 14–6: Hospital Anxiety and Depression Scale

Each item is scored from 0 to 3, with higher scores indicating more severe anxiety or depression. The total score for HADS-A and HADS-D will be derived by summing the scores over the 7 items and will range from 0 to 21.

In case of missing data, the following rules will be applied:

- If a maximum of 1 item is missing in HADS-A or HADS-D, the missing item will be imputed with the mean score from the remaining completed items within the HADS-A or HADS-D respectively.

- If more than 1 item is missing in HADS-A or HADS-D, the total HADS-A or HADS-D score will not be calculated.

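### Scoring a single unanswered DLQI question as 3 distorts change from Baseline in a direction set by the timing of the blank, and puts a total of 0 or 1 out of reach

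*SAP*

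**What the plan says.** SAP 14.3 sets the item rule: "If 1 question is left unanswered this question will be scored as 3". That score goes into the total. For more blanks it states: "If two or more questions are left unanswered a total DLQI will not be calculated". The rule does not distinguish Baseline from later visits, and the SAP gives neither a reason for it nor a sensitivity analysis. SAP 4.2.1 leaves missing data in the exploratory efficacy variables to the section on each variable, so this is the operative rule.

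Two neighbouring rules in SAP 14.3 matter here. An answer of 'Not relevant', offered for Questions 3 to 10, scores 0. A Question 7 answered 'No' with its second part left empty scores 3.

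SAP 8.3.6 gives the direction of the scale: "The total DLQI score ranges from 0 to 30 with higher scores indicating lower health related QoL". Besides the observed totals and their changes from Baseline, it tabulates two categories at each visit: "Total DLQI score of 0 or 1" and "Change from Baseline in the total DLQI score of -4 or below". The second is restricted to subjects with non-missing data "who had a total DLQI score of 4 or higher at Baseline". Protocol 9.7 explains the cut-offs: 4 points is reported as the within-subject minimal important difference, and 0 or 1 indicates no or small impact.

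For a single missing HADS item, SAP 14.5 takes a different course: "the missing item will be imputed with the mean score from the remaining completed items".

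**The concern.** Worst-score imputation looks cautious, but for a change score its direction depends on when the blank occurs. At Baseline it raises the starting point, and the subject appears to improve once the question is answered. After Baseline it hides real improvement. For the 0-or-1 category it acts as an automatic failure, whatever the other nine answers are.

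The rule also separates two subjects who may mean the same thing. One passes over the sport question because it does not apply and scores 3; another ticks 'Not relevant' and scores 0.

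At stake is the accuracy of the DLQI tables: mean change, the 4-point response rate and the 0-or-1 rate, with about 20 subjects in each of two arms.

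**Working it through.** **Inputs.** Ten items (SAP 14.3: "The 10 questions and scoring of the DLQI are presented in" Table 14–3), each scored 0 to 3; one blank scores 3; response is a change of -4 or below among those with a Baseline total of at least 4; about 20 placebo, 20 adalimumab and 40 bimekizumab subjects (SAP 2.3).

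**The plan's own figure.** 10 × 0 = 0 and 10 × 3 = 30, which reproduces the stated range of 0 to 30.

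**Effect on change.** Let x be the true answer to the blank item, with that item answered at the other visit.
- Baseline blank: recorded change = true change - (3 - x).
- Post-Baseline blank: recorded change = true change + (3 - x).

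| True answer x | Error size, 3 - x | True change needed for response, Baseline blank | True change needed, post-Baseline blank |
|---|---|---|---|
| 0 | 3 | -1 | -7 |
| 1 | 2 | -2 | -6 |
| 2 | 1 | -3 | -5 |
| 3 | 0 | -4 | -4 |

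The largest error is 3, or 3/4 = 75% of the threshold. If the same item is blank at both visits, the two 3s cancel and the change rests on the other nine items.

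**Entry to the response denominator.** Take a true Baseline total of 3 with a true-zero item left blank. It is recorded as 3 + 3 = 6, so the subject enters the denominator. A later complete total of 2 gives 2 - 6 = -4, a recorded response after a true change of 2 - 3 = -1. Low Baseline totals are not needed for the threshold effect. With an illustrative true Baseline of 12 and a true-zero blank, the record is 15; a later total of 11 gives -4 against a true -1.

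**The 0-or-1 category.** The minimum total with one blank is 9 × 0 + 3 = 3. A true total of 0 is recorded as 3. A true total of 1 is recorded as 3 if the blank item held the point, and as 4 if it did not.

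**Size in an arm.**
- One 3-point error moves a 20-subject mean by 3/20 = 0.15 and a 40-subject mean by 3/40 = 0.075.
- One misclassified subject already in a denominator of 20 moves the rate by 1/20 = 5 percentage points.
- If the subject also wrongly enters the denominator as a responder, the rate goes from r/19 to (r + 1)/20, a shift of (19 - r)/380. With r = 10 (assumed), 52.6% becomes 55.0%, or 2.4 points; 5 points arises only at r = 0.
- With fewer than 20 eligible subjects, the step of 1/n is correspondingly larger.

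**Alternative rule.** Impute the mean of the nine answered items, so total = S × 10/9, where S is their sum.

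| S | Current rule, S + 3 | Mean rule | Mean rule, rounded |
|---|---|---|---|
| 0 | 3 | 0 | 0 |
| 1 | 4 | 1.11 | 1 |
| 4 | 7 | 4.44 | 4 |
| 9 | 12 | 10 | 10 |
| 18 | 21 | 20 | 20 |
| 27 | 30 | 30 | 30 |

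Without rounding, S = 1 gives 1.11 and still misses 0 or 1. Rounding is therefore part of the repair.

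**The case against.** The strongest reply is that little depends on this. DLQI is exploratory, SAP 3.1 confines formal testing to the primary variable, and neither the HiSCR analysis nor the success criterion uses DLQI. The rule is the same in every arm of a subject-blind study, and nothing in the documents suggests that blanks would differ by arm. Each question is listed by subject and visit, so blanks can be found and totals recalculated, and the data evaluation meetings consider missing values. All of this stands and limits the severity.

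It can also be said that scoring a post-Baseline blank as the worst answer is cautious, in the spirit of non-responder imputation for HiSCR. That holds for post-Baseline blanks only; at Baseline the same rule works the other way.

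A reader might infer that the HADS rule shows the SAP contradicting itself. It does not: HADS has separate seven-item subscales, and item rules may differ between instruments. It is an analogy showing that the SAP already accepts mean imputation elsewhere. Whether the DLQI rule agrees with the instrument's own scoring guidance cannot be judged from these documents.

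The DLQI rules might be defended as consistently worst-case, since the incomplete Question 7 also scores 3. They are not wholly so: a mark between two boxes takes the lower score.

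**Conclusion.** The point stands at low severity. Followed as written, the rule gives a wrong item score whenever the true answer to the single blank is below 3. The error in the change score is up to 3 points, towards improvement for a Baseline blank and towards worsening for a later one, provided the item is answered at the other visit. The artefact cannot create a 4-point response from no change, but it lowers or raises the true change required by up to 3 points. That one blank excludes a total of 0 or 1 follows from the arithmetic and needs no assumption.

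A reader might go further and infer that the DLQI comparison between arms is biased, or biased in favour of bimekizumab. The documents do not support that: they give no rate of blank items and no reason for the rate to differ by arm or visit, so the group-level effect cannot be calculated. Nor does every Baseline blank create false improvement; none arises if the true answer was 3, and the imputed values cancel if the item is blank at both visits. The 5-point figure per subject is the maximum for a denominator of 20, not a typical effect.

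**What to change.** In SAP 14.3:
- Replace the single-blank sentence with: if 1 question is unanswered, impute it with the mean of the other 9 item scores and round the total to the nearest integer.
- Treat Question 7 with an incomplete second part as an unanswered question under the same rule, instead of scoring it 3. Otherwise the two kinds of blank would be handled differently within one instrument.
- Keep the rule that two or more unanswered questions give no total.

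A count of imputed items by arm and visit would show whether the matter had any practical effect. If the sponsor prefers to retain the score of 3, the SAP should give the reason and report that count.

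The cost is an amendment of two sentences, a rounding convention and a few lines of derivation code. SAP Section 1 already requires an amendment when analysis definitions change before database lock. The mean rule is not free of error: nine zeros with a blank whose true answer was 3 would be recorded as 0. But its error is not always in the direction of a worse score, and it leaves every total category attainable.

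### A DLQI Question 7 answered No with its second part left blank is scored 3, the score for Yes and above the 0 to 2 that a completed No can receive

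*SAP*

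**What the plan says.** Question 7 has two parts (SAP Table 14–3). The first asks whether skin prevented work or study, with the options Yes, No and Not relevant. A subject who answers No is then asked how much of a problem it was, with the options A lot, A little and Not at all.

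The scoring rules below that table read as follows.

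- Yes: "If Question 7 is answered “Yes” this will be scored as 3".
- The No branch opens with "If question 7 is answered “No” the scoring will be as follows" and has two sub-rules. The first is "If “A lot”, “A little” or “Not at all” is ticked this will be scored as 2, 1 or 0 respectively". The second is "If the second half of the questions is left incomplete, the score will be set to 3".
- Not relevant: "If a question is answered as “Not relevant” then this will be scored as 0".
- Missing items in general: "If 1 question is left unanswered this question will be scored as 3", and "If two or more questions are left unanswered a total DLQI will not be calculated".

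SAP 8.3.6 uses the total in three ways: summary statistics for observed values and changes from Baseline; the percentage of subjects with a total of 0 or 1; and the percentage whose change is -4 or lower, among those with a Baseline total of at least 4. Protocol 9.7 describes a 4-point change as meaningful to the subject.

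**The concern.** The second sub-rule sits under the No branch, so it applies to a subject who has already said that skin did not prevent work or study. The value assigned is the one reserved for the opposite answer. The follow-up has no option worth 3, so no completed No can produce it. The rule discards information the subject gave.

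At stake are the DLQI total at each affected visit and the two categorical summaries built on it. Their cut-offs (1 point and 4 points) are small enough for an error of 1 to 3 points on one item to change a subject's classification.

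**Working it through.** **Inputs.** All scores come from SAP 14.3, and the cut-offs from SAP 8.3.6.

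| Question 7 response | Score |
|---|---|
| Yes | 3 |
| No, A lot | 2 |
| No, A little | 1 |
| No, Not at all | 0 |
| Not relevant | 0 |
| No, second part blank | 3 |

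**Excess on the item.** Let q be the score a completed follow-up would have given. The excess is e = 3 − q. For q = 2, 1, 0 this gives e = 1, 2, 3.

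**Range of the total.** With a completed No the maximum is 9 × 3 + 2 = 29. With No and a blank it is 9 × 3 + 3 = 30, the same as for a subject who answered Yes.

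**Total of 0 or 1.** With No and a blank the smallest total is 0 + 3 = 3, so the subject cannot be counted in this category at that visit, even with 0 on the other nine items.

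**Change of -4 or lower.**

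- Blank only after Baseline: recorded change = true change + e. A true response is lost if it is -4 (e = 1), -4 or -5 (e = 2), or -4 to -6 (e = 3).
- Blank only at Baseline: recorded change = true change − e. A non-response becomes a response if the true change is -3 (e = 1), -3 or -2 (e = 2), or -3 to -1 (e = 3).
- Blank at both visits: the two 3s cancel. The error is q at Baseline minus q after Baseline, which can be zero.

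**Denominator (Baseline total of at least 4).** Let S be the Baseline sum of the other nine items.

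- S = 1: a completed No gives 1, 2 or 3, so the subject is ineligible. A blank gives 1 + 3 = 4, so the subject is eligible. If the later total is 0, the recorded change is 0 − 4 = -4, a response.
- S = 2 or 3: eligibility depends on q if the follow-up is completed, and is certain if it is blank.
- S = 0, or S of 4 or more: the blank makes no difference to eligibility.

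**Interaction with the missing-item rule.** Suppose Question 7 is half completed and one other item is wholly blank. If Question 7 counts as unanswered, no total is calculated. If it does not, a total is calculated that includes 3 + 3 = 6 assigned points. The SAP does not say which applies.

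**The case against.** The best defence is that the 3 follows a convention. SAP 14.3 gives a single wholly unanswered item the worst score, and the Question 7 line carries that over to a half-completed item. The rule is prespecified and applies equally to all arms. It also follows that any subject with one blank item, whichever it is, has a total of at least 3 and cannot reach 0 or 1, so that consequence is not peculiar to Question 7.

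This explains where the 3 comes from but does not justify it. The item was not wholly unanswered, and the worst case consistent with No is 2. Nor is the section worst-case throughout: a mark between two boxes takes the lower score. When two boxes are ticked the higher score is used, but that is still a response the subject marked.

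Three stronger readings are tempting, and the documents do not support them.

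- A reader might infer that the rule always makes DLQI results look worse. It raises the total at the affected visit, but a blank only at Baseline makes improvement look larger.
- A reader might infer that skipped follow-ups are common among subjects with no work problems. Neither document gives a rate, and subjects to whom the item does not apply can choose Not relevant, which scores 0.
- A reader might infer that the mean imputation used for HADS (SAP 14.5) is the natural repair. It belongs to another instrument, and it can exceed 2: if the other nine items all score 3, the mean is 27 / 9 = 3. Simply declaring the item unanswered would also return it to 3 under the DLQI's own rule.

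**Conclusion.** The point holds as a scoring inconsistency. A recorded No with a blank follow-up gets a score outside the range the SAP allows for No: 1 to 3 points too high on the item and on the total at that visit. The effect on change from Baseline can go either way, by 1 to 3 points when only one of the two visits is affected, against a 4-point threshold.

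This rests on reading the second sub-rule as part of the No branch. Its placement supports that, although its wording, which refers to questions in the plural, is loose.

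The practical weight is low. DLQI is an exploratory variable (SAP 2.2.1.2) summarized descriptively, and formal testing is confined to the primary variable (SAP 3.1). HiSCR and the success criterion are untouched. If nobody skips the follow-up, the effect is nil. The documents give no basis for inferring a bias between arms.

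**What to change.** Replace the 3 in the second sub-rule with one explicit value between 0 and 2, after checking the instrument's scoring instructions. The documents alone do not settle which value. If the worst-case convention is to be kept, 2 is the value consistent with it. In that case the item can still be up to 2 points too high, and the smallest total is 0 + 2 = 2, so the subject still cannot reach the 0 or 1 category. The SAP should say that this is accepted.

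In the same amendment, state whether a half-completed Question 7 counts as unanswered under the rule for two or more missing items. Do not bring in the HADS mean.

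The cost is a one-line correction and one clarifying sentence, made through the SAP amendment that SAP section 1 requires when a definition changes before database lock. If the DLQI outputs are already programmed, rerun them and report the number of affected records by arm and visit. That count would also show whether the rule mattered.
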